**Table 7-2 Management of immune-related AEs**

NCI-CTCAE grade v5.0	Suggested management	Suggested follow-up
Gastrointestinal immune-related AEs: diarrhea and/or colitis		
Grade 1 Diarrhea: <4 stools/day over baseline Colitis: asymptomatic	
 
• May continue nivolumab therapy
 
• Evaluate symptomatic treatment (e.g. loperamide)
 
	
 
• Close monitoring for symptoms worsening
 
• Educate patient to report if worsening immediately
 
• If worsens: treat as Grade 2 or 3/4
 
• GI consultation may be needed for persistent cases (e.g. more than 4 weeks)
 

Grade 2 Diarrhea: 4 to 6 stools per day over baseline; IV fluids indicated <24 h; not interfering with activities of daily living Colitis: abdominal pain; blood in stool	
 
• Withhold temporarily nivolumab therapy until resolution to Grade 1
 
• Symptomatic treatment if infection is ruled out
 
• Consider GI consultation
 
• Consider 1 mg/kg/day prednisone or equivalent
 
	
 
• If improves to Grade ≤1: resume nivolumab therapy
 
• If persists ≥3 to 5 days or recurs: treat as Grade 3 or 4
 

Grade 3 to 4 Diarrhea (grade 3): ≥7 stools per day over baseline; incontinence; IV fluids ≥24 h; interfering with activities of daily living Colitis (grade 3): severe abdominal pain, medical intervention indicated, peritoneal signs Grade 4: life-threatening, perforation	
 
• Withhold temporarily nivolumab therapy for Grade 3, if first occurrence.
 
• Permanently discontinue study treatment for Grade 4 or recurrent Grade 3.
 
• 1 to 2 mg/kg/day prednisone IV or equivalent
 
• Add prophylactic antibiotics for opportunistic infections
 
• Consider lower endoscopy
 
• Consider early infliximab treatment (5-10 mg/kg) if symptoms are steroids-refractory after 2-3 days.
 
	
 
• If improves: continue steroids until Grade 1, then taper over at least 4-6 weeks; resume nivolumab therapy following steroids taper (for initial Grade 3).
 
• If worsens, persists ≥2 to 3 days, or recurs after initial improvement: add infliximab (5-10 mg/kg, if no contraindication)
 

NCI-CTCAE grade v5.0	Suggested management	Suggested follow-up
Skin immune-related AEs		

Grade 1 to 2
	
 
• Continue nivolumab therapy
 
• Symptomatic therapy and advise to avoid sun exposure (for example, oral antihistamines, topical emollients and/or medium to high-potency topical steroids, as appropriate)
 
	
 
• If persists >1 to 2 weeks or recurs: consider withholding nivolumab therapy until resolution to Grade ≤ 1 and monitor weekly; consider skin biopsy
 
• Consider 0.5 to 1.0 mg/kg/day prednisone or equivalent. Once improving, taper steroids over at least 1 month, consider prophylactic antibiotics for opportunistic infections, and resume nivolumab therapy following steroids taper
 
• If worsens: treat as Grade 3 to 4
 

Grade 3
	
 
• Withhold temporarily nivolumab therapy for Grade 3 first occurrence.
 
• Permanently discontinue study treatment for recurrent Grade 3.
 
• Consider skin biopsy
 
• Dermatology consultation
 
• 1 to 2 mg/kg/day prednisone or equivalent
 
• Add prophylactic antibiotics for opportunistic infections
 
	
 
• If improves to Grade ≤1: taper steroids over at least 1 month; resume nivolumab therapy following steroids taper (for initial Grade 3)
 

Grade 4 Life threatening consequences or all severe rashes unmanageable with prior interventions
	
 
• Permanently discontinue study treatment
 
• Admission and urgent dermatology consultation
 
• IV (methyl)prednisolone 1-2 mg/kg or equivalent
 
• Add prophylactic antibiotics for opportunistic infections
 
• If bullous pemphigoid is diagnosed, treatment with rituximab maybe considered instead of long-term steroids
 
	
 
• Slow tapering over more than one month upon resolution
 

NCI-CTCAE grade v5.0	Suggested management	Suggested follow-up
Pulmonary immune-related AEs: Pneumonitis		

Grade 1 Asymptomatic, radiographic changes confined to one lobe or <25% of lung parenchyma only
	
 
• Consider withholding nivolumab therapy if radiologic evidence of pneumonitis progression
 
• Monitor oximetry, history and physical exam + chest radiography weekly
 
• Consider pulmonary and infectious disease consultations
 
	
 
• Re-assess CT scan if available at baseline at least 3-4 weeks, spirometry/ diffusing capacity of the lungs for carbon monoxide (DLCO)
 
• Resume nivolumab upon radiologic improvement or resolution
 
• If no improvement: treat as Grade 2 or Grade 3 to 4
 

Grade 2 Symptomatic, involves more than one lobe or 25-50% of lung parenchyma
	
 
• Withhold nivolumab therapy until resolution to Grade 1 or less
 
• Pulmonary and infectious disease consultations
 
• Monitor symptoms daily, consider hospitalization
 
• 1.0 to 2.0 mg/kg/day prednisone or equivalent
 
• Add prophylactic/empirical antibiotics for opportunistic infections
 
• Consider bronchoscopy with bronchoalveolar lavage (BAL)
 
	
 
• Re-assess every 3 days
 
• If improves: when symptoms return to Grade ≤1, taper steroids by 5-10 mg/wk over 4-6 wks and then resume nivolumab therapy following steroids taper
 
• If not improving after 48-72 h of steroids or worsening: treat as Grade 3 to 4
 

Grade 3 to 4 Grade 3: Severe new symptoms; New / worsening hypoxia; Grade 4: Life-threatening
	
 
• Permanently discontinue study treatment
 
• Hospitalize
 
• Pulmonary and infectious disease consultations
 
• 1.0 to 2.0 mg/kg/day prednisone or equivalent
 
• Add prophylactic antibiotics for opportunistic infections
 
• Consider bronchoscopy with BAL ± lung biopsy
 
	
 
• If improves to Grade ≤1: taper steroids over at least 4-6 weeks.
 
• Add infliximab 5 mg/kg or mycophenolate mofetil IV 1.0 g twice daily or IV immunoglobulins for 5 days or cyclophosphamide, if not improving after 48 h of prior steroids
 

NCI-CTCAE grade v5.0	Suggested management	Suggested follow-up
Hepatic immune-related AEs: Liver Test Elevation		

Grade 1 Asymptomatic, AST or ALT up to 3.0 x ULN (1.5 – 3.0 x baseline if baseline was abnormal) or total bilirubin up to 1.5 x ULN (>1.0 - 1.5 x baseline if baseline was abnormal)
	
 
• Continue nivolumab therapy
 
• Educate the patient to report symptoms immediately
 
	
 
• Continue liver function monitoring at least once or twice weekly
 
• If worsens: treat as Grade 2 or Grade 3 to 4, as appropriate
 

Grade 2 Asymptomatic AST or ALT >3 to 5 x ULN (>3.0 - 5.0 x baseline if baseline was abnormal) and / or total bilirubin >1.5 to ≤3 x ULN (> 1.5 – 3.0 x baseline if baseline was abnormal)
	
 
• Withhold nivolumab therapy temporarily
 
• Increase frequency of monitoring to every 3 days
 
• Advise to stop unnecessary medications and known hepatotoxic drugs
 
• May consider low dose prednisone (≤10 mg/d or equivalent)
 
• Symptomatic patients may consider prednisone 0.5-1.0 mg/kg/d or equivalent
 
	
 
• If returns to Grade ≤1: resume routine monitoring, may resume nivolumab therapy after steroids tapering.
 
• If elevations persist ≥3 to 5 days, or if worsens: treat as Grade 3 to 4
 
• If improvement on steroids consider tapering over 4-6 weeks (re-escalate if needed)
 


Grade 3 to 4 (immune-related possible, probable or likely) AST or ALT > 5 x ULN (>5.0 x baseline if baseline was abnormal) and /or total bilirubin >3 x ULN or symptomatic liver failure (e.g. ascites, coagulopathy, encephalopathy or coma)
	
 
• Permanently discontinue study treatment
 
• Increase frequency of monitoring to every 1 to 2 days
 
• Start immediately 1 to 2 mg/kg/day (methyl)prednisolone or equivalent
 
• Add prophylactic antibiotics for opportunistic infections
 
• Consult hepatologist if no improvement on steroids
 
• Consider obtaining MRI/CT scan of liver and liver biopsy if clinically warranted
 
	
 
• If returns to Grade ≤1: taper steroids over at least 1 month
 
• If does not improve in ≥3 to 5 days, worsens or rebounds: add mycophenolate mofetil or azathioprine or other non-hepatotoxic systemic immunosuppressants
 
• Avoid use of infliximab in the context of suspected immune-mediated hepatitis
 

NCI-CTCAE grade v5.0	Suggested management	Suggested follow-up
Renal immune-related AEs		
Grade 1	
 
Consider holding nivolumab therapy, while excluding alternative causes
 
	
 
Re-assess renal function regularly
 
If worsens: treat as Grade 2, 3 or 4
 

Grade 2	
 
Withhold nivolumab therapy temporarily
 
Nephrology consultation
 
Increase frequency of monitoring to every 2-3 days
 
0.5 to 1.0 mg/kg/day prednisone or equivalent.
 
Add prophylactic antibiotics for opportunistic infections
 
Consider renal biopsy
 
	
 
If returns to Grade <math>\leq 1</math>: Taper steroids over at least 1 month, and resume nivolumab therapy following steroids taper
 
If worsens or no improvement on steroids: 1-2 mg/kg/d prednisone or equivalent and treat as Grade 3-4
 

Grade 3-4	
 
Permanently discontinue study treatment
 
Monitor creatinine daily
 
1-2 mg/kg/d prednisone or equivalent.
 
Add prophylactic antibiotics for opportunistic infections
 
Consider renal biopsy
 
Nephrology consultation
 
	
 
If returns to Grade <math>\leq 1</math>: Taper steroids over at least 4 weeks and consider mycophenolate mofetil
 

Cardiac immune-related AEs (myocarditis, pericarditis, arrhythmias, impaired ventricular function with heart failure and vasculitis)		
Grade 1 Any abnormal cardiac biomarker testing, including abnormal ECG	
 
Withhold nivolumab temporarily until further work-up to exclude alternative causes
 
Hospitalize
 
Consult cardiologist to establish etiology and rule out immune-mediated myocarditis
 
Guideline-based supportive treatment as per cardiology consultation*
 
Consider early starting of high-dose steroids (1-2 mg/kg/d orally or IV depending on situation)
 
	
 
Consider permanent nivolumab discontinuation even upon resolution
 

NCI-CTCAE grade v5.0	Suggested management	Suggested follow-up

Grade <math>\geq 2</math> Grade 2 : any abnormal test with mild symptoms
	
 
• Permanently discontinue study treatment
 
• Guideline-based supportive treatment and further workup as appropriate as per cardiology consultation*
 
• Start 1-2 mg/kg/d (methyl)prednisolone IV or equivalent
 
• In the presence of life threatening cardiac decompensation, consider transfer to a facility experienced in advanced heart failure and arrhythmia management
 
	
 
• Once improving, taper steroids over at least 4-6 weeks
 
• If no immediate improvement or worsening, consider methylprednisolone at 1 g/d and/or add additional immunosuppressants either mycophenolate mofetil, infliximab, antithymocyte globulin
 

Endocrine immune-related AEs		

Grade 1 or Grade 2 endocrinopathies (hypothyroidism, hyperthyroidism, adrenal insufficiency, type I diabetes mellitus)
	
 
• May continue nivolumab therapy
 
• Endocrinology consultation if needed
 
• Start thyroid hormone replacement therapy (for hypothyroidism), anti-thyroid treatment (for hyperthyroidism), corticosteroids (for adrenal insufficiency) or insulin (for type I diabetes mellitus) as appropriate.
 
• Rule out secondary endocrinopathies (i.e. hypopituitarism / hypophysitis)
 
	
 
• Continue hormone replacement/suppression and monitoring of endocrine function, as appropriate
 

Grade 3 or Grade 4 endocrinopathies (hypothyroidism, hyperthyroidism, adrenal insufficiency, type I diabetes mellitus)
	
 
• Withhold nivolumab therapy
 
• Consider hospitalization
 
• Endocrinology consultation
 
• Start thyroid hormone replacement therapy (for hypothyroidism), anti-thyroid treatment (for hyperthyroidism), corticosteroids (for adrenal insufficiency) or insulin (for type I diabetes mellitus) as appropriate
 
• Rule out secondary endocrinopathies (i.e. hypopituitarism / hypophysitis)
 
	
 
• Resume nivolumab once symptoms improve to Grade <math>\leq 1</math> or patient stabilizes with hormone replacement
 
• Continue hormone replacement/suppression and monitoring of endocrine function, as appropriate
 

Hypopituitarism/Hypophysitis (secondary endocrinopathies)
	
If secondary thyroid and/or adrenal insufficiency is confirmed (i.e. subnormal serum free thyroxine (FT4) with inappropriate low thyroid-
	
 
• Resume nivolumab once symptoms and hormone tests improve to Grade <math>\leq 1</math> (with or without hormone
 

NCI-CTCAE grade v5.0	Suggested management	Suggested follow-up
	
stimulating hormone (TSH) and/or low serum cortisol with inappropriate low adrenocorticotrophic hormone (ACTH):
 
 
• Refer to endocrinologist for dynamic testing as indicated and measurement of other hormones (follicle-stimulating hormone (FSH), luteinizing hormone (LH), growth hormone (GH)/ insulin-like growth factor 1 (IGF-1), prolactin (PRL), testosterone in men, estrogens in women)
 
• Hormone replacement/ suppressive therapy as appropriate
 
• Perform pituitary MRI and visual field examination as indicated
 
 
If hypophysitis confirmed:
 
 
• Continue nivolumab if mild symptoms with normal MRI. Repeat the MRI 1 month later
 
• Withhold nivolumab if moderate, severe or life-threatening symptoms of hypophysitis and/or abnormal MRI. Consider hospitalization. Initiate corticosteroids (1 to 2 mg/kg/day prednisone or equivalent) followed by corticosteroids taper during at least 1 month.
 
• Add prophylactic antibiotics for opportunistic infections.
 
	
replacement)
 
 
• In addition, for hypophysitis with abnormal MRI, resume nivolumab only once shrinkage of the pituitary gland on MRI/CT scan is documented.
 
• Continue hormone replacement/suppression therapy as appropriate.
 

Neurologic immune-related AEs		

Grade 1 neurologic toxicities or Grade ≤2 peripheral neuropathy or mood changes
	
 
• Withhold nivolumab therapy temporarily
 
• Close monitoring for worsening symptoms
 
	
 
• If persistent: initiate prednisone or equivalent at 1.5 mg/kg/day
 
• Consider resuming nivolumab therapy after discussion with the patient about the benefit/risk balance.
 
 
If peripheral neuropathy improves to Grade ≤ 1 and does not reoccur after steroids taper: resume nivolumab therapy

NCI-CTCAE grade v5.0	Suggested management	Suggested follow-up

Grade 3-4 and/or any other Grade 2 other than peripheral neuropathy, mood changes
	
 
• Permanently discontinue study treatment
 
• Patient's hospital admission in facilities with availability of assisted mechanical ventilation (AMV)
 
• Urgent neurologic and intensive care consultation
 
• Initiate therapy with high-dose IV steroids and other symptomatic and supportive treatment as needed
 
	
Musculoskeletal immune-related AEs		

Grade 1
	
 
• Continue nivolumab therapy
 
• If CPK is elevated and/or symptomatic: start oral corticosteroids and treat as Grade 2
 
	

Grade 2
	
 
• Withhold nivolumab temporarily and may resume upon resolution to Grade 1
 
• Add low doses of prednisone <10 mg
 
• Rheumatologic or neurologic consultations
 
	
 
• If worsened: treat as Grade 3
 

Grade 3-4 or if CPK ≥ Grade 2
	
 
• Permanently discontinue study treatment
 
• Hospital admission in facilities with availability of AMV
 
• Urgent neurologic and intensive care consultation
 
• Start immediately 1mg/kg prednisone or equivalent
 
• Consider further supportive symptomatic treatment including plasmapheresis if severe compromise (weakness severely limiting mobility, cardiac, respiratory, dysphagia)
 
• Referral for neurology or rheumatology admission
 
	

NCI-CTCAE grade v5.0	Suggested management	Suggested follow-up
Hematologic immune-related toxicities (out of immune diseases such as autoimmune hemolytic anemia, acquired thrombocytopenia)		
Grade 1	
 
• May continue nivolumab therapy
 
	
 
• Monitor for improvement closely (i.e., weekly)
 

Grade 2	
 
• Withhold nivolumab therapy temporarily
 
• Start prednisone at 1.5 mg/kg/d
 
	
 
• May resume nivolumab if improvement or no worsening after steroids tapering
 

Grade 3 – 4	
 
• Permanently discontinue study treatment
 
• Hematologic consultation and consider hospitalization
 
• Initiate prednisone at 1 mg/kg/d or equivalent
 
• Start rituximab therapy and IVIG (if applicable)
 
• Consider blood transfusion as per existing guidelines
 
	
Ocular immune-related toxicities		
Grade 1 asymptomatic	
 
• Continue nivolumab therapy
 
• Refer to ophthalmology
 
	
 
• If symptomatic: add local treatment if indicated
 

Grade 2	
 
• Withhold nivolumab therapy temporarily
 
• Urgent ophthalmology referral
 
• Initiate topical steroids and consider systemic corticosteroids
 
• Re-treat after return to Grade 1 or less
 
	
 
• May resume nivolumab once off systemic corticosteroids, which are purely indicated for ocular AEs, or once corticosteroids for other concurrent systemic immune reaction AEs have been reduced to <math>\leq 10</math> mg
 

Grade 3 – 4	
 
• Permanently discontinue study treatment
 
• Urgent ophthalmology referral
 
• Initiate systemic corticosteroids 1-2 mg/kg or IV (methyl)prednisone
 
• Consider infliximab as per specialist evaluation
 
	

\*Local guidelines or e.g. American College of Cardiology (ACC) or American Heart Association (AHA) guidelines  
 European Society of Cardiology (ESC) guidelines website: <https://www.escardio.org/Guidelines/Clinical-Practice-Guidelines>  
 AHA guidelines website: [https://professional.heart.org/professional/GuidelinesStatements/UCM\\_316885\\_Guidelines-Statements.jsp](https://professional.heart.org/professional/GuidelinesStatements/UCM_316885_Guidelines-Statements.jsp)

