### 7.6.2.4. Management of immune-related adverse events

Since inhibition of PD-1/PD-L1 stimulates the immune system, immune-related AEs may occur. Adequate management and treatment of immune-related AEs provided below is mainly based on American Society

of Clinical Oncology (ASCO) practice guidelines recommendations (35) (but not only), depending upon severity (i.e., NCI-CTCAE grading), in general:

- Grade 1 to 2: treat symptomatically or with moderate dose steroids, more frequent monitoring
- Grade 1 to 2 (persistent): manage similar as to high -grade AE (grade 3 to 4)
- Grade 3 to 4: treat with high dose corticosteroids

Treatment of immune-related AEs should follow ASCO guidelines which are summarized in [Table 7-2](#).

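### The hematologic rows of Table 7-2 start prednisone at a higher dose for Grade 2 (1.5 mg/kg/d) than for Grade 3-4 (1 mg/kg/d), against the protocol's own gradient

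*Protocol*

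**What the plan says.** Protocol section 7.6.2.4 gives a general rule in words, without mg/kg figures. For low grades it says "Grade 1 to 2: treat symptomatically or with moderate dose steroids, more frequent monitoring"; for high grades, "Grade 3 to 4: treat with high dose corticosteroids". Between these sits a rule for low-grade events that do not settle: "Grade 1 to 2 (persistent): manage similar as to high -grade AE (grade 3 to 4".

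Table 7-2 then gives organ-specific advice. For hematologic events:

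- Grade 2: withhold nivolumab temporarily and "Start prednisone at 1.5 mg/kg/d". Nivolumab may restart if the event has improved, or merely not worsened, once steroids are tapered.
- Grade 3-4: stop study treatment permanently, obtain a hematology consultation, "Initiate prednisone at 1 mg/kg/d or equivalent", and add rituximab and IVIG if applicable.

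Section 5.4 describes immune-related holds of nivolumab as lasting until the event is back to at least Grade 1.

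**The concern.** A site that follows the table as printed starts more prednisone for the less severe hematologic event than for the more severe one. Nothing in the row explains this. The persistence rule could justify giving Grade 2 the same dose as Grade 3-4, but not a higher one, and the Grade 2 row is not limited to persistent events. At stake is either unnecessary steroid exposure at Grade 2 or too low a starting dose at Grade 3-4, depending on which figure is the slip.

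The resumption wording raises a smaller question. It lets nivolumab restart while the event may still be Grade 2, which is looser than section 5.4.

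**Working it through.** **Size of the inversion.** Inputs are the two hematologic cells of Table 7-2. Ratio = 1.5 / 1.0 = 1.5, so the Grade 2 start is 50% above the Grade 3-4 start. In mg/d (dose per kg × weight):

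| Weight | Grade 2 | Grade 3-4 | Difference |
|---|---|---|---|
| 80 kg (Protocol section 2.1) | 120 | 80 | 40 |
| 50 kg (assumed lower end) | 75 | 50 | 25 |
| 100 kg (assumed upper end) | 150 | 100 | 50 |

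The mg/d figures only rescale the same ratio; they are not separate evidence.

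**Is the hematologic group unusual?** These are all the organ groups in Table 7-2 that give mg/kg doses at two severity levels:

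| Group | Lower level (mg/kg/d) | Higher level (mg/kg/d) | Direction |
|---|---|---|---|
| Gastrointestinal | 1 | 1-2 | rises |
| Skin | 0.5-1.0 | 1-2 | rises |
| Hepatic | 0.5-1.0 (symptomatic patients) | 1-2 | rises |
| Renal | 0.5-1.0 | 1-2 | rises |
| Pulmonary | 1-2 | 1-2 | level |
| Cardiac | 1-2 | 1-2 | level |
| Hematologic | 1.5 | 1 | falls |

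Four rise, two are level and one falls. The renal Grade 2 entry, "0.5 to 1.0 mg/kg/day prednisone or equivalent", is typical of the rising groups. The low-grade neurologic row also uses 1.5 mg/kg ("If persistent: initiate prednisone or equivalent at 1.5 mg/kg/day"), but only for persistent events, and its high-grade row gives no mg/kg figure to compare.

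**Which cell is wrong?** The evidence points both ways.

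- Against the Grade 2 cell: the gastrointestinal, skin, hepatic and renal rows stop at 1.0 mg/kg/d at the lower level. The Grade 3-4 figure of 1 mg/kg lies at the bottom of the range that the cardiac Grade 1 row calls high-dose ("Consider early starting of high-dose steroids (1-2 mg/kg/d orally or IV depending on situation") and equals the musculoskeletal Grade 3-4 dose.
- Against the Grade 3-4 cell: the gastrointestinal, skin, pulmonary, hepatic, renal and ocular rows give 1-2 mg/kg at high grade, not a flat 1. Doses of 1 mg/kg or more at lower severity also occur elsewhere: pulmonary Grade 2, cardiac Grade 1, moderate hypophysitis and persistent low-grade neurologic events.

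**Resumption.** Six other rows with a firm Grade 2 hold of nivolumab tie restarting to Grade 1 or less: gastrointestinal, pulmonary, hepatic, renal, musculoskeletal and ocular. Skin is left out because it only suggests considering a hold. The low-grade neurologic row is mixed: it orders a hold that covers some Grade 2 events, allows resumption to be considered after a benefit/risk discussion, and ties only peripheral neuropathy to Grade 1 or less.

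Other rules block most early re-dosing. Table 5-3 requires hemoglobin of at least 9.0 g/dL for both drugs. For Debio 1143 on Days 1 and 15 it requires ANC of at least 1.5 and platelets of at least 100 ×10⁹/L, and Debio 1143-related events generally at Grade 1 or less. Section 5.4 holds nivolumab whenever Debio 1143 is held. Section 7.7.1 points to discontinuation, on risk/benefit grounds, if steroids above 10 mg/d are prolonged. What remains is an event that is still Grade 2, passes the Table 5-3 laboratory limits, is not attributed to Debio 1143, and is either asymptomatic or optimally treated.

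**The case against.** The table columns are headed as suggestions, and section 7.6.2.4 states its gradient only in general terms. It says the advice is mainly, not wholly, based on an external guideline, which cannot be consulted here and might support these doses. That stands as a reason to check before changing a figure. It does not remove the conflict, because the same section tells sites to treat according to the guideline that the table summarizes.

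Grade 3-4 care as a whole is stronger: permanent discontinuation, specialist consultation, and rituximab and IVIG if applicable. That also stands. A reader might infer that severe events are under-managed overall, or that a patient who worsens from Grade 2 should have prednisone cut from 1.5 to 1 mg/kg. The text supports neither: only the prednisone start is inverted, and the Grade 3-4 line sets a starting dose, not a reduction of one already running.

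A reader might also infer that the Grade 2 cell must be the mistake. The comparison above does not settle this. Cutting Grade 2 alone would be the wrong remedy if the Grade 3-4 figure is the slip.

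On resumption, a reader might infer that the hematologic row is the only loose one or that it opens a broad route to early re-dosing. The neurologic row contradicts the first inference. Table 5-3, the link between the two drugs and the persistence rule contradict the second.

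**Conclusion.** The inversion is on the face of the table and needs no assumption: 1.5 against 1 mg/kg/d, the only falling pair among seven organ groups, and contrary to the gradient in section 7.6.2.4. Which cell is wrong is open. The mg/d figures assume body weights of 80 kg and 50-100 kg; the documents do not say how many patients are affected.

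The resumption point survives only as an alignment with section 5.4 for a narrow residual case.

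This is a minor patient-safety wording correction. Sample size, decision boundaries, error rates and analyses are untouched. SAP section 4.3 describes the Part B cohorts as futile, so the benefit falls to anyone still on treatment and to any later protocol that reuses the table.

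**What to change.** 1. Correct the two hematologic cells so that the Grade 2 start does not exceed the Grade 3-4 start. The default consistent with the table's other rows is Grade 3-4 at 1-2 mg/kg/d and Grade 2 at no more than 1 mg/kg/d, for example 0.5-1.0 as in the skin, hepatic and renal rows. The clinical team should confirm both figures against the cited guideline before issue.
2. As a minor change, replace the hematologic Grade 2 condition for restarting nivolumab with resolution to Grade 1 or less after the steroid taper. No extra escalation line for persistent events is needed, because section 7.6.2.4 already covers them.

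The cost is wording in two rows at the next amendment and a clarification letter to sites. There are no extra patients, procedures or analyses.
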